10.2 SAFETY

Safety will be assessed by the rate of (number and percentage of subjects experiencing) device and/or procedure related adverse events after LINX

placement out to 12 months. Esophageal anatomy and functionality will be monitored by performing manometry and barium esophagram at 12-months post-implant. This will allow for identification of any abnormal or atypical findings. Further, device migration will be assessed by confirming device position at the GEJ by obtaining upright, bi-plane X-rays and device erosion will be assessed by performing endoscopy at the 12 month visit. Incidence of device migration and erosion will be compared to current incidence rates (i.e. zero documented incidents of device migration and a low but established occurrence of esophageal erosions) to assess concurrence of the safety profile of study subjects to that of patients without a prior LSG.

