11.9 ADVERSE EVENT REPORTING

If an intraoperative decision is made to not implant the LINX device, the subject will be monitored for procedure related adverse events for a period of at least three months (90 days) or longer if needed until resolution before withdrawing the subject from the study.

If a decision is made to explant the LINX device during the study, the subject will be monitored for explant-related adverse events for a period of at least three months (90 days) or longer if needed until resolution before withdrawing the subject from the study. No other study testing and/or questionnaires would be required after the device is explanted.

For all other subjects starting at the time of implantation and proceeding throughout the duration of the follow-up period, the Investigator will closely monitor each subject for the development of device and/or procedure related adverse events. A subject presenting with new onset dysphagia, abdominal pain, nausea, or vomiting, may be assessed for device migration and/or erosion if symptoms persist and benign causes cannot be established, at the discretion of the Investigator. This may include additional, non-study visit, x-rays or endoscopic evaluation. Adverse events will continue to be monitored at each of the study follow ups until resolution and/or study completion.

For the purposes of this study, a reportable event will be defined as any untoward medical occurrence which has a strong relationship to the LINX device and/or implant procedure and another etiology is unlikely. The Investigator must decide whether each event meets the definition of a Serious Adverse Event (SAE). All device and/or procedure related serious adverse events (SAE) must be reported immediately (within 5 days of discovery) to Torax Medical. SAE reporting to the IRB is per institutional policy.

An AE is considered **serious** if it meets one or more of the following criteria:

- **Is life-threatening or results in death**
Note: The term “life-threatening” in the definition of “serious” refers to an event in which the subject was at risk of death at the time of the event; it does **not** refer to an event that hypothetically might have caused death if it were more severe.
- **Requires subject hospitalization > 24 hours**
- **Requires prolongation of an existing hospitalization**
- **Results in persistent or significant disability/incapacity**
- **Results in fetal distress, fetal death, or a congenital anomaly or birth defect**

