Yes	xx (xx.x%)	xx (xx.x%)	xx (xx.x%)	xx (xx.x%)
No	xx (xx.x%)	xx (xx.x%)	xx (xx.x%)	xx (xx.x%)
No need to vomit	xx (xx.x%)	xx (xx.x%)	xx (xx.x%)	xx (xx.x%)
Ability to belch				
Yes	xx (xx.x%)	xx (xx.x%)	xx (xx.x%)	xx (xx.x%)
No	xx (xx.x%)	xx (xx.x%)	xx (xx.x%)	xx (xx.x%)

Denominator and percentages are based on subjects with non-missing data.

Table 18
 Regurgitation Severity Elimination from Severe and Moderate (Off PPI)
 Full Analysis Set

Change from Baseline	3 Months Follow-Up (N = ##)	6 Months Follow-Up (N = ##)	12 Months Follow-Up (N = ##)
Eliminate severe (to moderate, mild or none) [1]	xx (xx.x%)	xx (xx.x%)	xx (xx.x%)
Eliminate moderate (to mild or none) [2]	xx (xx.x%)	xx (xx.x%)	xx (xx.x%)

Column header counts represent the number of subjects who complete the FSQ form at the given visit.

[1] Percentages are calculated using the number of subjects with severe regurgitation at baseline and who complete the FSQ form at the given visit.

[2] Percentages are calculated using the number of subjects with moderate regurgitation at baseline and who complete the FSQ form at the given visit.

Table 19
 Regurgitation Frequency Summary (Off PPI)
 Full Analysis Set

Frequency	Baseline (N = ##)	3 Months Follow-Up (N = ##)	6 Months Follow-Up (N = ##)	12 Months Follow-Up (N = ##)
Regurgitation (times/week)				
n	xx	xx	xx	xx
Mean (SD)	xx.x (xx.x)	xx.x (xx.x)	xx.x (xx.x)	xx.x (xx.x)
Median (Min, Max)	xx.x (xx, xx)	xx.x (xx, xx)	xx.x (xx, xx)	xx.x (xx, xx)

Table 20
Adverse Events Summary
Full Analysis Set

Adverse Event Category	Number of Subjects (N = ##)	Number of Events
Any Adverse Events	xx (xx.x%)	xx
Serious Adverse Events	xx (xx.x%)	xx
AE related (Yes/Probably/Possibly or Unknown) to Study Device	xx (xx.x%)	xx
AE related (Yes/Probably/Possibly or Unknown) to Implant Procedure	xx (xx.x%)	xx
SAE related (Yes/Probably/Possibly or Unknown) to Study Device	xx (xx.x%)	xx
SAE related (Yes/Probably/Possibly or Unknown) to Implant Procedure	xx (xx.x%)	xx

All percentages are calculated using the number of subjects in the FAS as the denominator.

Table 21
All Adverse Events
Full Analysis Set

Adverse Event Category	Number of Subjects (N = ##)	Number of Events
Total	xx (xx.x%)	xx
Achalasia	xx (xx.x%)	xx
Allergic reaction	xx (xx.x%)	xx
Anaphylaxis	xx (xx.x%)	xx
....	xx (xx.x%)	xx

All percentages are calculated using the number of subjects in the FAS as the denominator.

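### After explant, Protocol 11.9 narrows adverse event monitoring to undefined explant-related events and allows exit before 12 months, in conflict with the visit schedule and the 12-month safety rate

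*Protocol*

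**What the plan says.** Protocol 11.9 separates subjects by what happened to the device. On explant it says: "If a decision is made to explant the LINX device during the study, the subject will be monitored for explant-related adverse events". This lasts for a minimum of 90 days, longer where an event has not resolved, after which the subject is withdrawn. It adds: "No other study testing and/or questionnaires would be required after the device is explanted". The term explant-related is not defined.

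The next paragraph begins "For all other subjects starting at the time of implantation and proceeding throughout the duration of the follow-up period" and gives that group close monitoring for device- or procedure-related events. The section then defines a reportable event as "any untoward medical occurrence which has a strong relationship to the LINX device and/or implant procedure and another etiology is unlikely". The SAE sentence that follows refers to the device and the procedure without saying which procedure.

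Elsewhere the scope is wider. The schedule of data collection (Protocol synopsis, and Table 1 in section 7.0) marks device and procedure adverse events at implant and at every later visit through 12 months, with a footnote that the mark applies to every study subject. The synopsis and section 5.1 take safety to 12 months after implant, and section 5.1 lists device removals among the safety components. Section 10.2 counts subjects with "device and/or procedure related adverse events after LINX" placement over the same period.

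SAP 8.6 plans summaries of all AEs and SAEs, of those related to the device, and of those related to study procedures. In Table 20 the last category becomes "SAE related (Yes/Probably/Possibly or Unknown) to Implant Procedure", with a matching AE row. Percentages use the Full Analysis Set (FAS), which SAP section 6 identifies by the device having been implanted. SAP 8.9 summarises observed data only, without imputation.

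**The concern.** Two things do not fit together.

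First, a site is told to watch for explant-related events, but the definition of what it must report covers an event "which has a strong relationship to the LINX device and/or implant procedure". A complication of the removal operation alone is not clearly inside that definition. If it is recorded, Table 20 has no related-event row that plainly fits it.

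Second, explanted subjects are set apart from the sentence on device and procedure events and may leave after 90 days, although the safety rate runs to 12 months after implant. In the analysis they remain in the denominator for the whole period, and their unobserved months contribute no events.

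The stake is the related-SAE rate. The study aims to confirm safety similar to that behind the premarket approval, in at most 30 subjects, in support of a labelling change. Any loss of related events makes that rate look better, and it would fall on subjects whose device had to be removed.

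**Working it through.** The documents give no figure on this point to reproduce. The check has three parts.

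**1. The texts side by side**

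- Who is monitored for device and procedure events: 11.9 says those not explanted; the schedule footnote says all study subjects.
- For how long: 11.9 says at least 90 days after explant; the synopsis and sections 5.1 and 10.2 say to 12 months after implant.
- Which procedure: the 11.9 definition and Table 20 say implant; the SAE sentence in 11.9 leaves the word procedure open; SAP 8.6 says study procedures.

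These statements cannot all be followed for an explanted subject.

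**2. When an explanted subject can leave**

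Inputs: a 90-day minimum (Protocol 11.9); a 12-month window of Day 305 to Day 425 (Protocol Table 4); 30.4375 days per month (the SAP programming note on time to explant); 12 months taken as Day 365.

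Earliest exit day = explant day + 90.

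- Exit before the 12-month window opens: explant before Day 305 − 90 = Day 215.
- Exit before Day 365: explant before Day 365 − 90 = Day 275.

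Unobserved days = 365 − (month × 30.4375 + 90):

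| Explant at month | Earliest exit day | Unobserved days to Day 365 |
|---|---|---|
| 1 | 120 | 245 |
| 3 | 181 | 184 |
| 6 | 273 | 92 |
| 9 | 364 | 1 |

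These are upper values, because 90 days is a minimum and monitoring continues until resolution where needed.

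**3. Effect of one missed event**

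Assumption: N = 30 in the FAS, the planned maximum. One subject is 1/30 = 3.3 percentage points. Exact two-sided 95% upper limits:

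- 0/30: 1 − 0.025^(1/30) = 11.6%.
- 1/30: 97.5th percentile of Beta(2, 29) = 17.2%.

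A smaller analysis set makes the step larger; for example, 1/25 = 4.0 points.

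This step has a condition. Protocol 10.2 and SAP 8.6 count subjects, not events. If the explanted subject already has a related SAE, for instance the event that led to removal, a second one leaves the rate unchanged. The 3.3 points apply only to a subject with no related SAE already counted.

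**The case against.** The strongest reply is that the plan already has several ways to capture these events. It stands in part.

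- A reader might infer that removal complications have no reporting route at all. The documents do not support that. The SAE sentence in 11.9 does not limit procedure to the implant. The rule on unanticipated adverse device effects has no exception after explant. The AE form has an explant field. SAP 8.6 counts possible and unknown relatedness as related, so a removal complication could be classed as device related.
- A reader might infer that Table 20 shows only device and implant-procedure events. It also has rows for any AE and any SAE, and Table 21 lists all AEs. These rows can show only what sites record, however, and they do not give the related-SAE rate.
- A reader might infer that device events are lost from the moment of explant. The reportable-event definition carries no such exception, and the paragraph on the remaining subjects can be read as setting a monitoring schedule for each group. Loss is certain only after withdrawal.
- A reader might infer that the SAP has no explant summary. Part of the table shells, between Table 21 and the note before Table 29, is not in the text available, and that note describes how explants are identified and timed. Only the lack of an explant row in Table 20 can be stated.
- Some findings, such as migration on X-ray, cannot arise once the device is out, so the unobserved months are less informative than an equal period with the device in place.

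These points make the gap narrower. They do not reconcile 11.9 with the schedule or with the 12-month rate.

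**Conclusion.** The point holds as an inconsistency with a possible downward bias, and it should be corrected. Protocol 11.9, followed as written, leaves it unclear whether a removal-only complication is reportable or related. It also permits exit before Day 365 for any explant before Day 275, while the subject still counts in the FAS denominator.

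The unobserved time ranges from about 245 days (explant at month 1) to about 1 day (month 9), assuming withdrawal at the 90-day minimum. The effect on the related-SAE rate is 3.3 points per affected subject at an assumed N = 30, and only where that subject has no related SAE already counted.

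It would go too far to say that the rate is understated as a matter of fact. The documents do not state how many explants occur or when, and an affected subject may have no further event.

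**What to change.** - **Protocol 11.9.** Define explant-related. Reconcile the section with the schedule and the 12-month safety rate, so that the reportable-event and SAE wording covers the explant procedure as well as the device and the implant procedure.
- **Data collection.** Collect device- and procedure-related event status for explanted subjects to 12 months after implant, or to the end of the post-explant period if later. Section 7.0 already allows telephone follow-up, and this adds no testing or questionnaires. It concerns data collection only; clinical care after explant remains for the sponsor and investigators to settle.
- **SAP.** Align Table 20 with the study-procedures wording of section 8.6 by adding explant-procedure relatedness rows for AEs and SAEs. Count the SAEs in the overall device- and procedure-related SAE rate.
- **Subjects already withdrawn.** SAP 8.8 says that the initial enrolment of 30 was complete, so prospective contacts may come too late for some. For these, report the observed follow-up time and state the limitation beside the rate.

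The cost is a short clarification, one option on the AE form, the added table rows and a few telephone contacts. The SAE rate may come out slightly less favourable.

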11.10 SUBJECT COMPLETION AND WITHDRAWAL

All study subjects have the right to withdraw their consent to participate at any time during the study. Whenever possible, the site staff should obtain written documentation from the subject of his/her request to withdraw consent. If the site staff is unable to obtain written documentation, all information regarding the subject’s withdrawal must be recorded in the subject’s medical record.

On completion of the study (either by completion of protocol requirements or withdrawal), the Withdrawal/Completion CRF will be completed.

A subject may withdraw (or be withdrawn) from the study prematurely for the following reasons:

- Withdrawal of consent by subject
- Adverse event (Adverse Event Log or SAE CRF must be completed)
- Protocol deviation
- Lost to follow-up (In case of early withdrawal of a subject, at least three (3) documented attempts should be made to contact the subject and have them come into the clinic).
- Termination of study by the Sponsor
- Investigator believes it is in the best interest of the subject
- Other (must be specified)

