2.0 THE LINX REFLUX MANAGEMENT SYSTEM

2.1 DEVICE DESCRIPTION

The LINX® Reflux Management System is a laparoscopic, fundic-sparing anti-reflux procedure indicated for patients diagnosed with Gastroesophageal Reflux Disease (GERD) as defined by abnormal pH testing, and who are seeking an alternative to continuous acid suppression therapy (i.e. proton pump inhibitors or equivalent) in the management of their GERD. The LINX device is a permanent implant placed at the area of the lower esophageal sphincter (LES) and is designed to augment a weak LES and minimize or eliminate GERD-related symptoms.

[figure not shown]

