8.9 Handling of Missing Data

All summaries will be performed only on enrolled subjects and only observed data will be summarized. There will be no imputation of data for early terminated subjects or for missing data within the database.

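### A subject with the device in place can be withdrawn for an adverse event or a protocol deviation, and nothing then requires follow-up to 12 months

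*Protocol*

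**What the plan says.** Protocol 11.10 introduces its list with "A subject may withdraw (or be withdrawn) from the study prematurely for the following reasons". The list names an adverse event (which must be recorded on its form), a protocol deviation and the investigator's view of the subject's best interest, among others. It does not separate subjects who carry the device from those who do not. The same section says: "On completion of the study (either by completion of protocol requirements or withdrawal), the Withdrawal/Completion CRF will be completed".

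Protocol 11.9 gives the general rule for safety collection: "Adverse events will continue to be monitored at each of the study follow ups until resolution and/or study completion". It adds two special rules. A subject whose implant is abandoned during surgery is watched for procedure-related events for at least 90 days. After an explant, "the subject will be monitored for explant-related adverse events for a period of at least three months (90 days) or longer if needed until resolution", and then "No other study testing and/or questionnaires would be required after the device is explanted".

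Protocol 2.1 describes the device as permanent. The Synopsis sets the safety evaluation as the rate of serious device- and procedure-related events through 12 months.

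On analysis, SAP 8.9 summarises observed data only: "There will be no imputation of data for early terminated subjects or for missing data within the database". SAP Tables 6, 14 and 15 (pH, GERD-HRQL and PPI response) count only subjects with both baseline and 12-month data. Tables 9 and 16 (endoscopy and X-ray) use non-missing data. Tables 20 and 21 (adverse events) divide by the Full Analysis Set (FAS), which SAP section 6 identifies as every subject recorded as implanted.

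**The concern.** Leaving the study does not end exposure to a permanent implant. A subject withdrawn at month 4 for a troublesome adverse event still carries the device at month 12, but no rule makes anyone ask what happened in between.

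Two results are exposed. The first is 12-month efficacy: someone who leaves because of an adverse event is plausibly less likely than average to be a responder, and is dropped from the denominator. The second is safety. After the implant procedure, the schedule has one endoscopy, at 12 months, and one set of X-rays after the implant/discharge films, also at 12 months. A subject withdrawn earlier has no scheduled check for erosion or migration. Protocol 10.2 compares these incidences with a record of no migrations and few erosions, so a single missed case would matter. The results are meant to support a labelling change (Protocol 3.0).

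**Working it through.** **Step 1. What must be collected after withdrawal, by type of subject.**

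| Subject | Rule in Protocol 11.9 | Required to 12 months? |
|---|---|---|
| Implant abandoned in surgery | At least 90 days, procedure-related events | No |
| Device explanted | At least 90 days or until resolution, explant-related events; no further tests or questionnaires | No |
| Withdrawn with device in place | None stated; the general rule runs to resolution and/or study completion | No |

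The third row is the gap. The explant rule covers other subjects, and its minimum often falls short of 12 months: it reaches day 365 only for an explant on or after day 365 − 90 = 275, and the opening of the 12-month window only on or after day 305 − 90 = 215.

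**Step 2. Where that subject appears in the SAP tables.**
- Tables 6, 14 and 15: absent, because there are no 12-month data.
- 12-month columns of Tables 9 and 16: absent.
- Tables 20 and 21: in the denominator, with events recorded before withdrawal in the numerator. Time after withdrawal adds no events.

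**Step 3. Illustrative size for efficacy.** There is no plan figure to reproduce: the documents give no withdrawal count and no expected response rate, and SAP section 7 says the sample size was not calculated. Only N = 30 comes from the documents (the planned maximum). Assumptions: w = 2 or 4 withdrawn, none of whom would have responded, and about 80% response in the rest, with 70% and 90% as a range. With x responders among those remaining:
- printed rate = x / (30 − w)
- all-implanted rate = x / 30
- gap = printed rate × w / 30

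| Response in the rest | w | Printed | All implanted | Gap (points) |
|---|---|---|---|---|
| about 70% | 2 | 20/28 = 71.4% | 20/30 = 66.7% | 4.8 |
| about 70% | 4 | 18/26 = 69.2% | 18/30 = 60.0% | 9.2 |
| about 80% | 2 | 22/28 = 78.6% | 22/30 = 73.3% | 5.2 |
| about 80% | 4 | 21/26 = 80.8% | 21/30 = 70.0% | 10.8 |
| about 90% | 2 | 25/28 = 89.3% | 25/30 = 83.3% | 6.0 |
| about 90% | 4 | 23/26 = 88.5% | 23/30 = 76.7% | 11.8 |

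Exact (Clopper-Pearson) 95% intervals for the 80% rows are 59.0 to 91.7 against 54.1 to 87.7 (w = 2), and 60.6 to 93.4 against 50.6 to 85.3 (w = 4).

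The opposite extreme, in which every withdrawn subject would have responded, gives 24/30 = 80.0% against the printed 78.6%, and 25/30 = 83.3% against 80.8%. The printed rate would then be slightly low.

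**Step 4. Size for safety.** One subject whose first serious related event falls after withdrawal, and so goes unrecorded, lowers the reported rate by 1/30 = 3.3 points. If that would have been the only such event, 0/30 (exact upper limit 11.6%) is printed in place of 1/30 (upper limit 17.2%).

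**The case against.** A reader might infer that withdrawal ends safety collection in the subjects who do worst, or that every rate moves in the device's favour. The documents support neither.
- Explanted subjects, plausibly among the worst, must be monitored for at least 90 days before withdrawal. The SAP note on explants shows that some investigator withdrawals are explants and so fall under that rule.
- The event that prompts a withdrawal must be recorded, and it stays in Tables 20 and 21. Safety percentages count subjects, so someone withdrawn for a serious related event is already in the numerator. The 3.3 points need a first serious related event after withdrawal.
- A protocol deviation does not mark a subject as doing badly.
- A subject withdrawn for an adverse event may still have normal pH or be off PPIs.

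The efficacy contrast also compares observed cases with missing counted as failure. It therefore reflects the SAP's denominators as much as section 11.10. SAP 8.8 mentions disappointing early follow-up but gives no count and does not attribute it to these withdrawals.

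The statement that withdrawal is a form of completion comes from an instruction on when to fill in a form, and SAP Table 1 counts completers and withdrawals separately. Protocol 11.9 also speaks of monitoring through the whole follow-up period. So the text is silent about the time after withdrawal; it does not order collection to stop. The three contact attempts in 11.10 sit under loss to follow-up and do not amount to continued event collection.

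Finally, the study is descriptive, with no success threshold, and withdrawals are visible by reason in SAP Table 1 and by subject in Listing 22. A protocol deviation has no row of its own in Table 1, however, and would fall under the residual category.

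All of this limits the claim. None of it supplies a follow-up rule for a subject withdrawn with the device in place.

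**Conclusion.** The point stands in limited form and should be fixed. As written, the protocol allows withdrawal for an adverse event or a deviation and requires no further follow-up to 12 months while the device remains. The subject then drops out of the 12-month efficacy and imaging results, and is treated as event-free for unobserved time in the adverse event tables. This can understate the 12-month rate of serious related events and miss an erosion or migration.

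The direction is likely, but not certain, to favour the device when an adverse event is the reason; it is unknown when a deviation is. The size depends on the number withdrawn, which the documents do not give. Under the stated assumptions the efficacy gap is about 5 points for two withdrawals and 11 for four, with intervals that overlap widely. No pass or fail decision turns on a shift of that size, which is why this falls short of an essential correction.

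**What to change.** Amend Protocol 11.10 so that an adverse event or a protocol deviation is not a reason to end follow-up of a subject with the device in place. Such a subject stays in adverse event follow-up to 12 months and has whichever 12-month assessments he or she accepts, unless consent is withdrawn, the subject dies or is lost, or the study ends. Keep the investigator's judgement of best interest as a ground for omitting individual study tests, but not for stopping adverse event collection. The change concerns data collection only; it leaves clinical care and the right to withdraw consent as they are.

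SAP 8.8 says the initial enrolment of 30 was completed, so the amendment may come too late for some subjects. For those already withdrawn on these grounds, ask sites for adverse event status to 12 months where consent allows.

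The cost is an amendment with IRB approval (Protocol 11.4), a letter to sites, a few more contacts, and possibly less favourable rates.
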